DRUG IN RESEARCH AND REFERENCE, THERAPEUTIC REGIMEN AND ROUTE OF ADMINISTRATION	
Investigational medicine:
 
 1) Desamethasona (RECOVERY) 2) Methylprednisolone (BOLUS) 
Dose:
 
RECOVERY branch: Dexamethasone 6 mg/24h - 10 days (alternative Methylprednisolone 30mg/24h)
 
BOLUS: Methylprednisolone 250mg/ 24 hours - 3 days (alternative Dexamethasone 50mg/24h)
 
Administration: Intravenous administration. In the case of the RECOVERY branch, the investigator may prescribe oral administration if he considers it necessary from the third day of treatment.

HYPOTHESIS	
The use of high doses of bolus glucocorticoids will increase the anti-inflammatory effect without increasing side effects. This will allow a better evolution of patients, reducing the number of deaths and the need for intubation or admission to the Intensive Care Unit.

OBJECTIVES	
Primary:
 
To compare the effect of high-dose methylprednisolone boluses versus the dexamethasone intermediate dose regimen (RECOVERY trial) in COVID-19 patients with non-critical respiratory failure.
 
Side:
 
 • To assess the efficacy profile of the use of high-dose glucocorticoids for a short course on mortality in patients with COVID-19 • To assess the efficacy profile of the use of high-dose glucocorticoids for a short course on the evolution to need respiratory support (invasive mechanical ventilation or not) in patients with COVID-19 • To assess the efficacy profile of the use of high-dose glucocorticoids for a short course on the time of admission in patients with COVID-19 • To assess the safety profile of the administration of high doses of glucocorticoids in relation to the presence of added infections, hyperglycemia, psychotic symptoms or other adverse events.
DESIGN	
Clinical trial of low level of intervention, phase IV, open-label, randomized, comparison of 2 active treatments.

DISEASE OR DISORDER UNDER STUDY	COVID (coronavirus disease)
POPULATION AND TOTAL NUMBER OF PATIENTS	
Sample size: 290 (two groups of 145 patients)
 
Hospitalized patients, diagnosed with certainty of SARS-CoV-2 infection in acute phase (RT-PCR-or antigen positive) who have respiratory failure.

SELECTION CRITERIA	
Inclusion criteria:
 
 1. Over 18 years old. 2. Hospitalized patient. 3. Diagnosis of SARS-CoV-2 infection confirmed by RT-PCR or antigen. 4. Computed tomography (CT) evidence of lung involvement attributed to COVID infection is presented. Patients in whom CT is not performed should have suspicion of pulmonary involvement by clinically with compatible or suggestive simple radiology. 5. Requires supplemental oxygen by basal saturation $\leq 93\%$ (with ambient O₂, 21%) 
Exclusion criteria:
 
 1. The patient's situation is so serious that the doctor responsible thinks he could die in the next 24 hours. 2. Patients require at randomization one of the following 4 ventilatory supports: 
 • High Oxygen Flow Devices • Non-invasive mechanical ventilation • invasive mechanical ventilation • extracorporeal membrane oxygenation (ECMO). 3. The patient is or has been treated in the 2 weeks prior to randomization with glucocorticoids or inflammation-modifying drugs, both conventional (thiopurines, cyclophosphamide, cyclosporine, tracolimus, leflunomide, methotrexate, mycophenolate mofetil / mycophenolic acid, sulfasalazine, hydroxychloroquine or chloroquine) and synthetic or biological directed against therapeutic targets (abatacept, belimumab, CD-20, IL1, IL6, IL12.23, IL-23, IL-17, TNF, integrin $\alpha 4\beta 7$ or JAK inhibitors). 4. The patient is pregnant or breastfeeding 5. The patient has stage 4 or 5 chronic kidney disease (rCC <30 ml/min) 6. Moderate to severe dementia at the discretion of the investigator. 7. Hypersensitivity to any of the active ingredients or to any of the excipients included in its formulation. 8. Untreated systemic infections not caused by COVID-19. 9. Active stomach ulcer or duodenal ulcer.

	10. Recent vaccination with live vaccines. 11. There is another infection or disease that explains the lung disorder 12. Inability of the patient to understand the study or sign the informed consent unless a consent delegated to a legal representative is made. 13. Active participation in another clinical trial in the past 15 days
VISIT PROGRAMME	Selection Visit Randomization Day 4-6 (any day between 4 and 6) Day 12-16 (any day between the 12th and the 16th) Day 28 (window allowed: d24-d30) 3 months (window allowed: \pm 2weeks) Visit to discharge or premature withdrawal
TRIAL SCHEDULE	Recruitment is planned to begin in December 2020. The overall duration of the study is estimated at approximately 9 months, from the start of the recruitment period (6 months of recruitment) to the last follow-up visit (3 months of follow-up). This study is expected to be completed in September 2021.

1.3. Reference CEIm

Salamanca Health Area.

1.4. Study phase.

Phase IV clinical trial.

1.5. Name and title of the Study Coordinator, address and contact details.

[name], graduate specialist in Internal Medicine, Internal Medicine Service, Río Hortega University Hospital. Associate Professor of the degree of Medicine at the University of Valladolid
Río Hortega University Hospital, [name].
[contact], [name]
Email: [contact]
[contact]

1.6. Participating centers.

1. Río Hortega University Hospital
2. University Assistance Complex of Salamanca
3. University Clinical Hospital of Valladolid

4. University Assistance Complex of Burgos
5. University Assistance Complex of León

4. Introduction and justification of the study

At the end of December 2019, cases of viral pneumonia caused by previously unknown people in the city of Wuhan China began to be described. A few weeks later, severe acute respiratory syndrome coronavirus 2 (SARS-CoV-2) was isolated for the first time, and the disease was referred to as COVID-19. Since then the virus has been spreading and causing a global epidemic that has overwhelmed global health systems and for which there is still no established cure.

During the first phase of the pandemic, different therapeutic approaches were used, mainly aimed at preventing both the viral phase (the virus entering cells or replicating) and a second phase of severe inflammation. This second phase is characterized by a marked elevation of acute phase reactants and the development of adult respiratory distress syndrome. To stop this second phase, different immunomodulatory treatments have been tested, including glucocorticoids.

The RECOVERY¹ study has demonstrated the usefulness of an intermediate regimen of dexamethasone in critically ill patients with SARS-CoV-2 infection and less markedly in patients who need oxygen but are not in critical condition. Another 3 studies in critically ill patients (CoDEX², CAPE-COVID³, REMAP-CAP-COVID⁴) have confirmed these results. In severe but non-critical patients, GLUCOCOVID⁵ demonstrated improvement in a combined endpoint (death, ICU admission, mechanical ventilation) with an intermediate dose of glucocorticoids (GC). The METCOVID⁶ study, however, has not refuted these data with a 5-day course of methylprednisolone at intermediate-high doses (see Figure 1 and Table 1).

[figure not shown]
On the other hand, uncontrolled observational studies have shown possible improvement with the use of higher doses of GC during a short cycle instead of the intermediate dose⁷⁻⁹.

The pathophysiological explanation for this possible improved higher dose response would be activation of the non-genomic GC activation pathway. GCs exert their action in two ways, genomics and non-genomics. The mechanisms of this second way are not fully defined^{10,11}. The genomic pathway is responsible for the classic immunomodulatory and anti-inflammatory action of GCs and the main side effects, glycemic, lipid and bone. The non-genomic pathway is mediated by the interaction of GCs with a specific membrane receptor that is particularly expressed in inflammatory cells. This pathway begins to be activated with boluses, but not with intermediate doses. Activation of this pathway could justify improved bowing response.

Table 1. GC randomized clinical trials guidelines in COVID.

I am a student	Agenda	Equivalent in prednisone day	Days
RECOVERY	Dexamethasone 6 mg/24h	DXA 6 mg = 30 mg	10 days
METCOVID	Methylprednisolone 0.5 mg/kg/12h	Patient type 70 kg MP 70 mg = 87,5 mg	5 days
GLUCOCOVID	Methylprednisolone 40 mg/12h x 3 days and then 20 mg/12h x 3 days	MP 80 mg = 100 mg	6 days
CoDEX	Dexamethasone 20 mg/24h x 5 days Dexamethasone 10 mg/24h x 5 days	DXA 20 mg= 125 mg DXA 10 mg= 62,5 mg	10 days
REMP-CAP C	Hydrocortisone 50-100mg/6h x 7 days	HDC 200 mg = 50 mg	7 days
CAPE COVID	Hydrocortisone 200 mg/24h x7 days, then 100 mg/24h x4 days, Then 50 mg/24hh x 3 days.	HDC 200 mg = 50 mg	14 days (8 if good evolution)

Figure 1. Results of the different studies published with CG in covid-19

5. Objective and Purpose of the Test

5.1. Hypothesis of the study.

The use of high doses of bolus glucocorticoids will increase the anti-inflammatory effect without increasing side effects. This will allow a better evolution of patients, reducing the number of deaths and the need for intubation or admission to the Intensive Care Unit.

5.2. Main objective.

To compare the effect of high-dose methylprednisolone boluses versus the dexamethasone intermediate-dose regimen (RECOVERY trial) in non-critical COVID-19 patients with respiratory failure.

5.3. Secondary objectives:

- To assess the efficacy profile of the use of high-dose glucocorticoids for a short course on mortality in patients with COVID-19.

- To assess the efficacy profile of the use of high doses of glucocorticoids for a short cycle on the evolution to need respiratory support (invasive mechanical ventilation or not) in patients with COVID-19.
- To assess the efficacy profile of the use of high-dose glucocorticoids for a short course on the time of admission in patients with COVID-19.
- To assess the safety profile of the administration of high doses of glucocorticoids in relation to the presence of added infections, hyperglycemia, psychotic symptoms or other adverse events.

6. Trial Design

Low-intervention clinical trial, phase IV, open-label, randomized, comparison of 2 active treatments.

[Justification for the low level of intervention: paragraph 8.3 of this Protocol and Annex 2]

6.1. Selection and Randomization

Action	Responsible
1. Inclusion of the patient in the study	The doctor who attends the patient is the one who decides the need to prescribe corticosteroids and informs the patient to propose their inclusion in the study
2. Patient randomization	It will be carried out centrally through the electronic data collection notebook (CRDe). Eligible subjects will be randomly assigned 1:1 to the two treatment groups.
3. Implementation of treatment.	Once the patient is randomized, the doctor will prescribe the treatment as usual, which will be prepared and dispensed in each center according to the usual practice of the same.

Since randomization is centralized and through the CRDe, the treatment list of patients is not accessible to researchers, so they do not know a priori what may be the treatment arm assigned to each patient.

7. Selection and Withdrawal of Subjects

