8.1. Characteristics of the Research Product

Methylprednisolone boluses are currently a common treatment in diseases with a serious component of infamatio such as lupus nephritis. That is why its application in the inflammation phase of COVID could be useful, since these patients have a severe inflammatory profile. The response to intermediate doses of dexamethasone suggests a possible effect of treatment with higher doses.

The risks of corticosteroid treatment at the bolus dose in the short term are similar to those of administration of intermediate doses, with an increased risk of bacterial superinfection, baseline glycemic decompensation, or risk of psychosis or arousal. Use in cycles of a few days has no long-term side effects such as hypertension, dyslipidemia or osteoporosis.

The chosen pattern is the same as that used in acute inflammatory diseases, such as lupus nephritis. In case of lack of stock, it could be decided to use other glucocorticoid preparations in doses equivalent to that of methyl-prednisolone, according to the following table:

Table 2. Guidelines equivalences to methylprednisolone in different studiess.

Active substance	Agenda	Equivalence in methyl-prednisolone	Equivalence in prednisona
Dexamethasone	6 mg/24h	30 mg/24h	37,5mg/24h

Metilprednisolona	250mg/24h	N/A	312,5 mg/24h
Hidrocortisona	50-100mg/6h	20-40 mg/12h	25-50 mg/12h

Reference: doses calculated according to "Steroid Conversion Calculator", accessible in <https://www.mdcalc.com/steroid-conversion-calculator#evidence>

Patients with a confirmed diagnosis of SARS-CoV-2 who have pulmonary involvement and are at risk of developing adult respiratory distress syndrome will be included.

There are studies that have evaluated observationally the treatment with GC boluses in this pathology in which there seems to be a beneficial effect when compared with the usual treatment (Callejas-Rubio, Rodríguez-Baño, Ruiz-Irastorza).

8.2. Treatment groups and selected doses.

Patients continue with the treatment that is considered standard in their center and associate glucocorticoids in 2 possible regimens (group membership is done randomly)

- 1) RECOVERY guideline. Intravenous administration of 6mg of dexamethasone every 24h for 10 days. It can be given both orally and intravenously at the same dose
- 2) BOWLING GUIDELINE. Intravenous administration of 250mg of methylprednisolone every 24 hours for 3 days.

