8.4. Concomitant treatments

8.3.1. Concomitant treatment allowed (Standard Treatment)

Although this is a pragmatic study in real practice and some degree of heterogeneity is accepted in standard treatment, minimum requirements are considered to be able to include patients in the study. Thus, as standard treatment is accepted:

- a) Supplemental oxygen. For use in patients with hypoxemia. The target for oxygen therapy should not exceed 92% in patients at risk of respiratory failure with hypercapnia and 96% in all other patients.
- b) Antibiotic treatment. Standard treatment protocols should not recommend the administration of empirical antibiotic treatment on a routine basis. Its administration should only be recommended when risk of bacterial pneumonia is considered as co-infection. The antibiotic regimen will correspond to the usual treatment guide of the center.
- c) Prophylaxis or thromboembolism treatment with low molecular weight heparins. Thrombotic prophylaxis is recommended in all admitted patients and the use of therapeutic doses in patients with confirmed thromboembolic disease. The use of extended prophylaxis guidelines could be assessed according to the recommendations of the Spanish society of thrombosis and hemostasis.

- d) Remdesivir. The use of remdesivir is accepted if it is done according to the recommendations of the Ministry of Health.
- e) Other antiviral drugs or drugs that block viral activity. The protocols should not incorporate the following drugs: Hydroxychloroquine or chloroquine, lopinavir-ritonavir.
- f) Serum therapy. The use of serum therapy is allowed in those indications defined in the protocols.
- g) Other concomitant medications without antiviral or immunosuppressive effect (eg: antihypertensives, analgesics, lipid-lowering agents, antiplatelet agents,...). There is no limitation to the use of these drugs.

8.3.2. Concomitant treatments prohibited.

Other immunosuppressants. The concomitant use of other immunosuppressants is NOT allowed in the first 48 hours of evolution. If immunosuppressants are prescribed during the study, patients in whom they are initiated with the third or subsequent dose of CG should be maintained. The use of these drugs in these patients will be considered as an event.

9. Development of the study.

9.1. Study schedule.

Recruitment is planned to begin in December 2020.

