11.3. Statistical analysis

The categorical variables will be presented as frequency and percentage and the continuous variables as mean and standard deviation.

Death after 28 days, intubation or admission to the ICU will be presented as proportions. The difference in proportions will be estimated with a 95% confidence interval.

An analysis per protocol will be performed, considering those patients who have received at least 2 doses of the assigned drug. In addition, an intention-to-treat analysis will be carried out.

In the event that there is a depletion of stock and any of the guidelines are replaced by one of the alternatives proposed in point 8.2, no adjustment would be made in the analysis since the equivalence of dose and dosage between the original dose and the substitution is established.

For the analysis of the main outcome, death at 28 days, survival analysis will be performed and the Hazard ratio of the Cox regression, with the log-rank statistic, will be used to estimate the mortality relationship.

An alpha error of 5% is set.

In case there was a lack of balance in the age of the patients between the groups, age-adjusted analyses would be performed, establishing 2 groups: < 70 years and \geq 70 years.

Two interim efficacy and safety analyses are established with 100 and 200 patients

2 analyses of the results are established according to:

- a) Time of evolution (<7 days from the onset of symptoms, \geq 7 days from the onset of symptoms).
- b) Presence of a state of high inflammation. The patient is considered to have a high degree of inflammation when he meets any of the following laboratory criteria:
 - Ferritin greater than or equal to 1000 mg/dl
 - IL-6 greater than or equal to 20 pg/ml
 - PCR mayor o igual a 150 mg/l
 - D-dimer greater than or equal to 1000 mg/dl

Finally, since no age criterion is established to exclude older patients, a sensitivity analysis will be performed, leaving out those patients who had orders of no intubation or non-invasive mechanical ventilation prior to being included in the study.

For statistical analysis, the IBM SPSS statistics, version 21 program will be used.

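### The allocation method is not specified and the primary Cox/log-rank analysis ignores centre, so between-centre variation and chance centre imbalance stay in an otherwise valid comparison

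*Combined protocol and SAP*

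**What the plan says.** Section 1.6 lists five participating hospitals. Section 6 describes the design as "Low-intervention clinical trial, phase IV, open-label, randomized, comparison of 2 active treatments". Section 6.1 places randomisation in the central electronic notebook, with a treatment list that investigators cannot see: "Eligible subjects will be randomly assigned 1:1 to the two treatment groups". It names no stratification factor, block size or minimisation scheme. The same section has the attending doctor decide that corticosteroids are needed and propose the patient for the trial.

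On background care, section 8.2 says: "Patients continue with the treatment that is considered standard in their center and associate glucocorticoids in 2 possible regimens". Section 8.3.1 limits this: "some degree of heterogeneity is accepted in standard treatment, minimum requirements are considered to be able to include patients in the study". It then sets conditions on antibiotics, heparin prophylaxis and remdesivir and keeps certain antivirals out of local protocols. Section 8.3.2 restricts other immunosuppressants early on.

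For the primary outcome, death at 28 days, section 11.3 says "the Hazard ratio of the Cox regression, with the log-rank statistic, will be used to estimate the mortality relationship". No centre term or centre strata appear. The only adjustment planned is for age in two groups, and only if age turns out unbalanced. Interim analyses are set at 100 and 200 patients.

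**The concern.** The protocol itself makes centre a likely source of outcome differences, because background care is partly local. ICU admission, ventilatory support and time to discharge plausibly follow local practice too, although that is a judgement and not something the documents state. A known source of variation that enters neither the allocation nor the analysis costs precision. If one arm happens to receive more patients from a high-mortality centre, that difference goes into the hazard ratio uncorrected.

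The missing allocation method matters separately, because the right analysis depends on it. If the central system already balances by centre, the test should reflect that. If it does not, centre imbalance is left to chance.

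**Working it through.** **Plan's own figure.** Section 11.1 gives 28-day mortality of 23% and 10%, alpha 5% (taken as two-sided), beta 20% and 145 per group. With mean risk 0.165:

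- n = [1.96√(2 × 0.165 × 0.835) + 0.842√(0.23 × 0.77 + 0.10 × 0.90)]² / 0.13² = 127 per arm.
- With continuity correction, n = 142 per arm, within 3% of 145.
- Power at 145 per arm, without the correction, is 85.0%.

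The stated size reproduces and does not depend on centre. Expected deaths are 145 × 0.23 + 145 × 0.10 = 47.85, or about 9.6 per centre if centres are equal, which is enough for five strata.

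**Chance imbalance, if allocation were simple.** Assume five centres of 58. The chance that a given centre splits 36:22 or worse (binomial, 58, 0.5) is 8.7%. For at least one of five it is 1 − (1 − 0.087)⁵ = 36.5%. At the 100-patient interim, with 20 per centre, at least one splits 14:6 or worse with probability 46%.

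**Effect on the comparison.** The SD of the between-arm shift in expected mortality from centre mix is (SD of centre risks) × 2/√N. Centre risks are assumed; 17% and 37% are the lowest and highest of the three trial figures in section 11.1.

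- Control risk 17-29%: SD 0.5 points.
- 17-37%: 0.8 points.
- 10-37%: 1.1 points.
- 8-40%: 0.115 × 2/√290 = 1.35 points.

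The planned difference is 13 points, with standard error √[(0.23 × 0.77 + 0.10 × 0.90)/145] = 4.3 points. Even in the widest case, centre mix is 1.35²/4.3² ≈ 10% of the variance. At 100 patients, the 95th percentile of the shift runs from 1.7 to 4.4 points over these spreads.

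**Power.** Exponential deaths censored at day 28, 290 patients, HR = ln(0.90)/ln(0.77) = 0.403 unless noted, interim looks not simulated. Five equal centres except in the unequal-centre row.

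| Assumed control risk by centre | Simple allocation, unstratified test | Simple allocation, centre-stratified test | Blocked by centre, centre-stratified test |
|---|---|---|---|
| 23% in all | 85.6% | 85.3% | 86.3% |
| 17-29% | 86.5% | 86.3% | 86.9% |
| 17-37% (mean 25.4%) | 88.6% | 88.8% | 89.2% |
| 10-37% | 85.2% | 85.9% | 86.4% |
| Unequal centres, log-hazard SD 0.75 | 85.9% | 87.7% | 88.4% |
| 8-40% | 84.2% | 85.8% | 86.1% |
| 8-40%, HR 0.489 (23% vs 12%) | 67.3% | 70.1% | 70.6% |

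Runs per cell were 8,000 in the first four rows, 4,000 in the unequal-centre row and 6,000 in the last two. The standard error is about 0.4 to 0.5 points, or up to 0.6 in the last row, so changes below about one point between separate runs are noise. A separate 6,000-run check with no centre effect gave 85.7% and 85.3% for the outer two columns.

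Type I error is near 5% for the planned test under simple allocation and for the stratified test. Centre-blocked allocation followed by an unstratified test is slightly conservative: 4.1% in the 10-37% case.

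**Predictability.** With blocks of 4 and 6 within centre, a doctor who always guesses the arm that is behind in that centre is right about 69% of the time, against 50% under simple allocation. The strategy does not require knowing the block sizes.

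**The case against.** The strongest reply is that little is at stake. The shift from centre mix is already inside the standard error, the confidence interval covers it, and the test is valid. For spreads within the 17-37% range of the trials cited in section 11.1, the gain is 0.4 to 0.6 points of power. The top of the range needs an assumed 8-40% spread and a smaller effect than planned. All of this stands, and it limits the point to precision.

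Four stronger readings are tempting, and the documents do not support them:

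- **That 6.1 prescribes simple, unstratified allocation.** It does not say. The split probabilities above apply only if allocation is simple.
- **That background care is unrestricted.** Section 8.3.1 sets minimum requirements and exclusions. Local dispensing is not evidence that mortality differs.
- **That recruitment will come in waves and standard care will change.** Section 17 says only that a stable recruitment line is hard to establish and that treatments might be added or removed. A calendar-time benefit from blocking has not been quantified.
- **That balancing by centre is free.** It needs no extra patients. But the trial is open-label and the treating doctor proposes patients, so small blocks within centre open a possible route to selection bias. Undisclosed block sizes do not close it.

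**Conclusion.** The point holds as one of precision and specification. Section 6.1 leaves the allocation method open, and section 11.3 makes no use of centre although care is partly centre-specific. There is no bias and no type I inflation.

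Using centre in both allocation and analysis gains about 0 to 3 points of power at 290 patients. The gain is indistinguishable from zero when centres are similar and 1 to 3 points when they differ widely. In the wide-spread rows, about half or more comes from the analysis term, for example 0.7 of 1.2 points at 10-37%; simulation error makes that share approximate. If centres do not differ, the loss is not measurable. The conclusion rests on assumed centre risks, mostly equal centre sizes, a two-sided alpha and simple allocation as the comparator.

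**What to change.** **Section 11.3 (the main change).** Prespecify the primary Cox model and log-rank test as stratified by centre, and use the same test at the interim analyses. Include centre in the comparisons of ICU admission, ventilation and time to discharge. Fix this before anyone sees outcome data by arm. It costs one term per model and no patients, and can be adopted whatever the allocation method is.

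**Section 6.1.** State the allocation method. If it is or will be balanced by centre, describe a concealed scheme that limits predictability, such as minimisation with a random element or larger blocks of varying size. Blocks of 4 and 6 within centre should not be adopted as if costless. If allocation is already balanced by centre, the stratified analysis is needed to match it. The cost is a sentence in the protocol and, if the method changes, a setting in the central system. The sample size stays at 290.
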